### **5.8.3. Permitted Concomitant Medications**

Subjects will use background L-Dopa (for example, Sinemet, Menesit, Madopar, Prolopa, or EC Dopar) provided in the local commercial packaging throughout the study. Subjects should remain on the same formulation of L-Dopa from Screening through the duration of the study. The daily L-dopa dose should not change from 21 days prior to Day 0 (Randomization) through the end of the study. In the case of unacceptable dopaminergic side

effects, and only following discussion with the Medical Monitor, the dose of L-Dopa may be reduced between the Day 1 and Day 105 visit.

Stable doses of concomitant medications for treatment of medical conditions are permitted during the course of the study, including antihypertensives, antidepressants (other than MAO inhibitors), anticoagulants, lipid lowering agents, oral antidiabetics, thyroid replacement hormones, and antacids.

The potential risk for drug-drug-interactions with PF-06649751 and primary substrates of CYP3A4 (especially those with a narrow therapeutic index; eg, vinca alkaloids), and BCRP is considered to be low, but cannot be excluded as it has not been fully evaluated at this time. Therefore, caution is recommended when PF-06649751 is combined with BCRP (eg, rosuvastatin, methotrexate, mitoxantrone, etc.) or CYP3A substrates (eg, alfentanil, ergotamine, irinotecan, ticagrelor, simvastatin, etc.). Further information on potential drug-drug-interactions and data available to date can be found in Section 5.2.7 Pharmacokinetic-Drug Interactions of the Investigator's Brochure.

### **5.9. Rescue Medication**

Rescue medication is permitted in the form of L-Dopa. The dose and dose frequency can be defined using investigator discretion based on patients' needs. Rescue L-Dopa may be administered if needed in between study visits based on a phone consultation and the discretion of the investigator.

## **6. STUDY PROCEDURES**

### **6.1. Screening: Day -45 to Day -1**

Subjects will be screened within 45 days prior to Day 0 (Randomization) to confirm they meet the subject selection criteria for the study. The investigator (or an appropriate delegate at the investigator site) will obtain informed consent from each subject in accordance with the procedures described in Section 12.3, [Subject Information and Consent](#). The informed consent may be obtained up to 60 days prior to Day 0 (Randomization).

The Screening procedures may be split between multiple days/visits for feasibility and/or subject comfort, however individual procedures should not be split between multiple days/visits.

The following procedures will be completed:

- Obtain written informed consent. For subjects needing further adjustment of concomitant medications, informed consent should be obtained prior to any adjustments and prior to the screening visit.
- Register subject as Screened in Interactive Web Response (IWR) system. Subjects will be assigned unique, 8-digit number, which will be retained throughout duration of study participation.

- Collect Demographics.
- Obtain prior medical history, medication history including current medications, and demography.
- Contraception Check.
- Assessment of prior/concomitant medications.
- Collect height, weight, and BMI.
- Perform full physical and neurological examination.
- Perform Mini Mental State Examination (MMSE).
- Confirm clinical diagnosis of Parkinson's disease using the UK Parkinson's Disease Society Brain Bank Clinical Diagnostic Criteria ([Appendix 6](#)).
- Perform Hoehn & Yahr Stage assessment while subject is ON.
- Collect blood and urine specimens for the following:
  - Safety laboratory tests (including specific tests for monitoring of vascular inflammation);
  - Serological testing (HIV testing, Hepatitis B antigen, and Hepatitis C antibody);
  - Urine drug screening test for drugs of abuse (including tetrahydrocannabinol (THC) performed at the central lab;
  - FSH test for females who are amenorrheic for at least 12 consecutive months. This is mandatory for female subjects that do not have documented hysterectomy, bilateral oophorectomy or medically confirmed ovarian failure, to confirm non childbearing potential (see [Section 4.1](#), Inclusion Criteria #3).
- Perform standard supine triplicate 12-lead electrocardiogram (ECG).
- Perform standard triplicate supine and standing vitals (heart rate (HR) and blood pressure) and assess subject temperature to confirm no symptoms of fever.
- Perform the Columbia Suicidality Severity Rating Scale (C-SSRS) "Lifetime/Past 12 months" Evaluation.
- Perform the Patient Health Questionnaire-8 (PHQ-8).

- Perform Movement Disorder Society-sponsored revision of the Unified Parkinson's Disease Rating Scale (MDS-UPDRS) Parts I, II, III, and IV (all parts to be completed on the same screening day).
- Train subject on OFF time recognition and OFF time diary (Hauser diary) with use of training video, and test concordance. Concordance testing includes at least one MDS-UPDRS Part III in the OFF state and one MDS-UPDRS Part III in the ON state (Part III score from full screening MDS-UPDRS may be used to fulfill one of these two exams, if the concordance assessment is continued/completed immediately after exam) which must be performed by the investigator (or qualified site staff/rater). At least 75% concordance with investigator (or qualified site staff/rater) for Screening ON/OFF time is required for eligibility (see [Section 7.1.7](#)).
- Dispense OFF time diary, review instructions including requirement to complete diary for 3 consecutive days in the week prior to Day 0 (Randomization).
- Instruct subjects on adjunct stable L-Dopa (open-label) administration.
- Review and assess adverse events (AEs).
- Review Inclusion and Exclusion criteria.

To prepare for study participation, subjects will be instructed on the use Section 4.4 and Section 5.8, [Lifestyle Guidelines](#) and [Concomitant Treatment\(s\)](#).

## 6.2. Study Period

For the study period described below, there is a +3 day visit window for scheduling of visits during Weeks 1, 2, and 3.

For Weeks 4-19, the visit window for scheduling visits will be  $\pm 3$  days.

**Study visit times are relative to Day 0 (Randomization), and not relative to when the previous visit actually occurred. The indicated visit windows are only intended to mitigate scheduling conflicts for study visits, and efforts should be made to return the subject to the correct timelines.**

For each visit, the following chronology of events should be adhered to, where possible:

- Patient Reported Outcome scales (ie, [CCI](#), [QUIP-RS](#), [CCI](#)): obtain prior to UPDRS.
- UPDRS Assessment: obtain prior to ECGs.
- ECGs: obtain prior to blood pressure and heart rate.
- Blood pressure/pulse rate: obtain prior to safety laboratory tests.

- Safety laboratory tests: obtain prior to pharmacokinetic (PK) blood.
- Pharmacokinetic blood specimens.
- Other procedures may be obtained before or after those listed above.

### 6.2.1. Randomization: Day 0

- Assessment of prior/concomitant medications.
- Review changes in medical history since screening visit.
- Review Inclusion and Exclusion criteria.
- Perform brief physical and neurological examination.
- Collect blood and urine for safety lab tests. Screening labs must have no clinically significant findings, as judged by the investigator, in order for the subject to be dosed with PF-06649751 or placebo.
- Urine drug screening in the form of a dipstick performed at the site.
- CCI [REDACTED]
- Collect Prolactin laboratory sample.
- Perform standard supine triplicate 12-lead electrocardiogram (ECG).
- Perform standard single supine and standing vitals (HR and blood pressure) and assess subject temperature to confirm no symptoms of fever.
- Perform the Columbia Suicidality Severity Rating Scale (C-SSRS) “Since last evaluation”.
- Collect and review OFF time diary while subject is present; confirm subject eligibility for OFF time has been met.
- Perform MDS-UPDRS I, II, III, and IV.
- CCI [REDACTED]
- CCI [REDACTED]
- CCI [REDACTED]

- CCI [REDACTED].
- CCI [REDACTED].
- Perform Questionnaire for Impulsive-Compulsive Disorders in Parkinson's Disease – Rating Scale (QUIP-RS).
- Perform Oral Symbol Digit Modality Test (SDMT).
- Perform Modified Clinical Global Impression - Severity (MCGI-S).
- CCI [REDACTED].
- Review and assess adverse events (AEs).
- Register subject as Randomized in IWR system in order to obtain randomization number.
- Dispense Investigational Product. Subjects will begin PF-06649751 or placebo dosing the following morning (Day 1).
- Instruct subjects on continued daily dosing of PF-06649751 or placebo in accordance with randomized dose arm up-titration scheme (see [Table 2](#), Section 5.5.1, [Titration of PF-06649751](#)) and instruct subjects on proper dosing documentation.
- Instruct subjects on continued adjunct stable L-Dopa (open-label) administration.

#### 6.2.2. Dosing: Day 1 through Day 105

- Continued once daily dosing of PF-06649751 or placebo in accordance with randomized dose arm up-titration scheme (see [Table 2](#), Section 5.5.1, [Titration of PF-06649751](#)).
- Continued adjunct stable open-label L-Dopa administration (through Period B).

#### 6.2.3. Titration Period: Day 7

- Dosing compliance verification (Investigational product accountability and documentation) while subject is present to confirm reasons for missed/additional doses. **Based on blister card review and/or tablet count, any subject who is noted not to have taken at least 80% or has taken more than 120% of required doses at any scheduled visit during the study will be considered out of compliance and this must be recorded on the CRF and documented as a Medication Error on the CRF and the source documents.**
- Review and assess adverse events (AEs).
- Assessment of concomitant medications.

- Perform the Columbia Suicidality Severity Rating Scale (C-SSRS) “Since last evaluation”.
- Perform standard supine triplicate 12-lead electrocardiogram (ECG).
- Perform standard single supine and standing vitals (HR and blood pressure).
- Perform MDS-UPDRS Part III.
- Dispense OFF time diary, review instructions including requirement to wait until the next phone visit before completion of the diary.
- Dispense Investigational Product. Next immediate dose level of PF-06649751 or placebo will be taken the next morning.
- Instruct subjects on continued daily dosing of PF-06649751 or placebo in accordance with randomized dose arm up-titration scheme (see [Table 2](#), Section 5.5.1, [Titration of PF-06649751](#)).
- Instruct subjects on continued adjunct stable L-Dopa (open-label) administration.

#### 6.2.4. Titration Period: Day 14

In the case of a phone visit:

- Dosing compliance verification via phone to confirm reasons for missed/additional doses. **Based on blister card review and/or tablet count, any subject who is noted not to have taken at least 80% or has taken more than 120% of required doses at any scheduled visit during the study will be considered out of compliance and this must be recorded on the CRF and documented as a Medication Error on the CRF and the source documents.**
- Review and assess adverse events (AEs).
- Assessment of concomitant medications.
- Instruct subjects on continued daily dosing of PF-06649751 or placebo in accordance with randomized dose arm up-titration scheme (see [Table 2](#), Section 5.5.1, [Titration of PF-06649751](#)).
- Instruct subjects on continued adjunct stable L-Dopa (open-label) administration.
- Inform the subject that the verification of blister card will be performed the day following the phone visit by the site staff by text, phone or email depending on the site/subject’s preference, and remind subjects to bring used blister cards to the next clinic visit.

- Review OFF time diary instructions including requirement to complete diary for 3 consecutive days during the following week.
- Dispense Investigational Product. Next immediate dose level of PF-06649751 or placebo will be taken the next morning following secure courier delivery.

In the case of a clinic visit:

- Dosing compliance verification (Investigational product accountability and documentation) while subject is present to confirm reasons for missed/additional doses. **Based on blister card review and/or tablet count, any subject who is noted not to have taken at least 80% or has taken more than 120% of required doses at any scheduled visit during the study will be considered out of compliance and this must be recorded on the CRF and documented as a Medication Error on the CRF and the source documents.**
- Review and assess adverse events (AEs).
- Assessment of concomitant medications.
- Collect blood and urine for safety lab tests.
- Perform standard supine triplicate 12-lead electrocardiogram (ECG).
- Perform standard single supine and standing vitals (HR and blood pressure).
- Perform the Columbia Suicidality Severity Rating Scale (C-SSRS) “Since last evaluation”.
- Dispense Investigational Product. Next immediate dose level of PF-06649751 or placebo will be taken on the next morning.
- Instruct subjects on continued daily dosing of PF-06649751 or placebo in accordance with randomized dose arm up-titration scheme (see [Table 2](#), Section 5.5.1, [Titration of PF-06649751](#)).
- Instruct subjects on continued adjunct stable L-Dopa (open-label) administration.
- Review OFF time diary instructions including requirement to complete diary for 3 consecutive days during the following week.

### 6.2.5. Titration Period: Day 21

In the case of a phone visit:

- Dosing compliance verification via phone to confirm reasons for missed/additional doses. **Based on blister card review and/or tablet count, any subject who is noted not to have taken at least 80% or has taken more than 120% of required doses at any scheduled visit during the study will be considered out of compliance and this must be recorded on the CRF and documented as a Medication Error on the CRF and the source documents.**
- Review and assess adverse events (AEs).
- Assessment of concomitant medications.
- Instruct subjects on continued daily dosing of PF-06649751 or placebo in accordance with randomized dose arm up-titration scheme (see [Table 2](#), Section 5.5.1, [Titration of PF-06649751](#)).
- Instruct subjects on continued adjunct stable L-Dopa (open-label) administration.
- Inform the subject that the verification of blister card will be performed the day following the phone visit by the site staff by text, phone or email depending on the site/subject's preference, and remind subjects to bring all used blister cards to the next clinic visit.
- Confirm the completion of the OFF time diary for 3 consecutive days during the past week and remind the subject to bring the completed diary to the next clinic visit.
- Dispense Investigational Product. Next immediate dose level of PF-06649751 or placebo will be taken the next morning following secure courier delivery.

In the case of a clinic visit:

- Dosing compliance verification (Investigational product accountability and documentation) while subject is present to confirm reasons for missed/additional doses. **Based on blister card review and/or tablet count, any subject who is noted not to have taken at least 80% or has taken more than 120% of required doses at any scheduled visit during the study will be considered out of compliance and this must be recorded on the CRF and documented as a Medication Error on the CRF and the source documents.**
- Collect and review OFF time diary while subject is present.
- Review and assess adverse events (AEs).
- Assessment of concomitant medications.

- Collect blood and urine for safety lab tests.
- Perform standard supine triplicate 12-lead electrocardiogram (ECG).
- Perform standard single supine and standing vitals (HR and blood pressure).
- Perform the Columbia Suicidality Severity Rating Scale (C-SSRS) “Since last evaluation”.
- Dispense Investigational Product. Next immediate dose level will be taken the next morning.
- Instruct subjects on continued daily dosing of PF-06649751 or placebo in accordance with randomized dose arm up-titration scheme (see [Table 2](#), Section 5.5.1, [Titration of PF-06649751](#)).
- Instruct subjects on continued adjunct stable L-Dopa (open-label) administration.

#### 6.2.6. Dose Adjustment: Day 28

- Dosing compliance verification (Investigational product accountability and documentation) while subject is present to confirm reasons for missed/additional doses. **Based on blister card review and/or tablet count, any subject who is noted not to have taken at least 80% or has taken more than 120% of required doses at any scheduled visit during the study will be considered out of compliance and this must be recorded on the CRF and documented as a Medication Error on the CRF and the source documents.**
- Collect and review OFF time diary while subject is present (if first clinic visit since Day 7).
- Review and assess adverse events (AEs).
- Assessment of concomitant medications.
- Perform standard supine triplicate 12-lead electrocardiogram (ECG).
- Perform standard single supine and standing vitals (HR and blood pressure).
- Perform the Columbia Suicidality Severity Rating Scale (C-SSRS) “Since last evaluation”.
- Perform MDS-UPDRS Part III.
- Dispense Investigational Product.

- Instruct subjects on continued daily dosing of PF-06649751 or placebo in accordance with randomized dose arm up-titration scheme (see [Table 2](#), Section 5.5.1, [Titration of PF-06649751](#)).
- Instruct subjects on continued adjunct stable L-Dopa (open-label) administration.
- Dispense OFF time diary, review instructions including requirement to complete diary for 3 consecutive days during the following week.

#### 6.2.7. Dose Adjustment: Day 35

- Dosing compliance verification (Investigational product accountability and documentation) while subject is present to confirm reasons for missed/additional doses. **Based on blister card review and/or tablet count, any subject who is noted not to have taken at least 80% or has taken more than 120% of required doses at any scheduled visit during the study will be considered out of compliance and this must be recorded on the CRF and documented as a Medication Error on the CRF and the source documents.**
- Collect and review OFF time diary while subject is present.
- Review and assess adverse events (AEs).
- Assessment of concomitant medications.
- Perform brief physical and neurological examination.
- Collect blood and urine for safety lab tests.
- Collect Prolactin laboratory sample.
- Perform standard supine triplicate 12-lead electrocardiogram (ECG).
- Perform standard single supine and standing vitals (HR and blood pressure).
- Perform the Columbia Suicidality Severity Rating Scale (C-SSRS) “Since last evaluation”.
- CCI [REDACTED]
- Perform MDS-UPDRS Parts I, II, III, and IV.
- CCI [REDACTED]
- CCI [REDACTED]

- CCI [REDACTED]
- CCI [REDACTED]
- CCI [REDACTED]
- Perform Questionnaire for Impulsive-Compulsive Disorders in Parkinson's Disease – Rating Scale (QUIP-RS).
- CCI [REDACTED]
- CCI [REDACTED]
- CCI [REDACTED]
- CCI [REDACTED]
- CCI [REDACTED]).
- Dispense Investigational Product.
- Instruct subjects on continued daily dosing of PF-06649751 or placebo in accordance with randomized dose arm up-titration scheme (see [Table 2](#), Section 5.5.1, [Titration of PF-06649751](#)).
- Instruct subjects on continued adjunct stable L-Dopa (open-label) administration.
- Dispense OFF time diary, re-watch instructional training video and review instructions including requirement to complete diary for 3 consecutive days during Week 10.

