6. FSH test at Screening is mandatory for female subjects that do not have documented hysterectomy, bilateral oophorectomy or medically confirmed ovarian failure, to confirm non childbearing potential (see [Section 4.1](#), Inclusion Criteria #3).
7. Hepatitis B antigen, Hepatitis C antibody, and HIV testing.
8. Urine test for drugs of abuse (including THC).
9. Triplicate ECG at all time points.
10. Triplicate vitals (HR and blood pressure) at Screening. Vitals should be collected first while the subject is in the supine position and then in the standing position. Subject temperature must also be assessed at Screening and Day 0 (Randomization) to confirm no symptoms of fever (see Exclusion Criteria #6).
11. Columbia Suicidality Severity Rating Scale (C-SSRS) "Lifetime/Past 12 months" evaluation at Screening, and Columbia Suicidality Severity Rating Scale "Since last evaluation" at all other time points.
12. Refer to [Section 7.2.1](#) for additional safety laboratory tests (blood and urine) to be completed at Screening and Week 17 follow-up visits, and/or as necessary throughout the study after consultation with the Medical Monitor/Sponsor per [Section 7.2.9](#).  
CCI [REDACTED]
14. Prolactin results may be shared with the blinded study team after database release.
15. In addition to compliance verification, subjects will be instructed on which blister card to use for following the week at each phone visit. The verification of blister card may be performed the day following the phone visits.
16. Visits should be scheduled at approximately the same time of day throughout the study. Subjects take their morning dose at home. Subjects will document the timing of PF-06649751 or placebo dose on study visit days.
17. First dose will be administered the morning of Day 1.  
CCI [REDACTED]
19. Diary training and concordance testing will be conducted during the screening visit, as detailed in [Section 7.1.7](#).
20. Subjects will complete an OFF time diary (Hauser diary) for three consecutive days in the week prior to Day 0 (Randomization) Visit and each diary review visit (except the Day 28 visit, in which the OFF time diary will be completed between Day 14 and Day 21 and brought the next clinic visit).
21. UPDRS Part III should be assessed consistently and approximately 2 to 4 hours following L-Dopa dose (except at Screening).

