## Appendix 7. Country-Specific Appendix - Japan

### Schedule of Activities and Study Procedures (Section 6)

For sites in Japan, the Week 2 (Day 14) and Week 3 (Day 21) visits during the Titration Period must be conducted as site (in-clinic) visits. Additionally, two phone visits are required a day after both the Day 0 (Randomization) Visit (Day 1) and Week 1 Visit (Day 7 [+3 day window]) and two additional study site visits are required a day after both Week 2 Visit (Day 14 [+3 day window]) and Week 3 Visit (21 [+3 day window]). Phone visits can optionally be conducted as site visits (eg, for logistical reasons). Subjects should be offered an optional overnight stay at the study site prior to a site visit. Study drug administration on both site visits (day after Week 2 Visit and Week 3 Visit) should occur at the study site. For phone visits, the phone calls should take place approximately 4 hours post-dose. During site visits, the study procedures are to be performed approximately 4 hours post-dose. Afterwards, subjects may be discharged at investigator's discretion if no safety concerns are identified. These visits (Day 1, Day 8, Day 15, and Day 22) are to be conducted in addition to the protocol [Schedule of Activities/Study Procedures \(Section 6\)](#).

Protocol Activity	Japan Specific Visits (including additional observation visits)					
	Rand. Visit	Wk 1 Observation Visit	Wk 2	Wk 2 Observation Visit	Wk 3	Wk 3 Observation Visit
	Day 1 (phone visit or optional site visit)	Day 8 (phone visit or optional site visit)	Day 14 (site visit)	Day 15 (site visit)	Day 21 (site visit)	Day 22 (site visit)
Concomitant medications assessment	X	X	X	X	X	X
AE assessment	X	X	X	X	X	X
Triplicate ECG			X	X	X	X
Supine and standing blood pressure and pulse rate			X	X	X	X
Columbia Suicidality Severity Rating Scale (C-SSRS)			X		X	
Safety Laboratory			X		X	
Dispensing of Investigational Product			X		X	
Investigational Product accountability			X		X	
Investigational Product and L-Dopa dosing documentation			X		X	
PF-06649751 (or placebo) administration	X	→	→	→	→	→
Adjunct L-Dopa (open-label)	→	→	→	→	→	→

### Day 1 and Day 8

- Assessment of concomitant medications.
- Review and assess adverse events (AEs).
- PF-06649751 or placebo administration in accordance with randomized dose arm up-titration scheme (see [Table 2](#), Section 5.5.1, [Titration of PF-06649751](#)).
- Instruct subjects on continued adjunct stable L-Dopa (open-label) administration.

### Day 14

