7. The daily OFF time for every rescue diary day will be replaced by the subject's baseline OFF time, that is, the baseline 3-day average. (All periods through Period A, and additionally Period B for subjects consented under Protocol Amendment 2 prior to entering Period B).

Daily Average (Rescue diary days are for all periods through Period A, and additionally Period B for subjects consented under Protocol Amendment 2 prior to entering Period B)

8. Valid home diary days (at least 12 awake hours, after all imputation) and/or rescue diary days will be used to compute the average daily OFF time. The valid home or rescue diary day must be within 7 days of the clinic visit (or phone visit for Week 3 only as noted below or assigned to the closest planned visit as noted below) but not on or after the day of the clinic visit. If more than 3 valid home or rescue diary days are available, the 3 days closest to the clinic visit will be used.
 - Prior to Protocol Amendment 2, the three consecutive days before Day 0 could occur anytime during the screening period and was not restricted to within a week of the visit. Therefore, all home diaries before Day 0 will be considered for Baseline, with the 3 days closest to Day 0 being used for analysis.
 - Subjects, who have a phone visit for Week 3 and their home diary collected at Week 4, will use their Week 3 phone visit to determine within 7 days.
 - If a valid home or rescue diary is considered for exclusion based on the "within 7 days" rule, it will still be included if its nominal visit is equal to the closest planned visit, otherwise it will be excluded. Planned visits: Baseline (Day -1), Week 3 (Day 21), Week 5 (Day 35) or Week 10 (Day 70).
 - i. Example 1: A subject who completed Week 3 diaries on Days 8, 9, and 10 with the actual Week 3 visit occurring on Day 21. All diaries excluded as all Week 3 diaries would all have been closer to Baseline (Day -1) than Week 3 (Day 21).

- ii. Example 2: A subject who completed Week 10 diaries on Days 61, 62 and 63 with the actual Week 10 visit occurring on Day 70. All diaries included because the diaries are closest to Day 70 which matches the clinic visit (Week 10).
 - iii. Example 3: A subject who completed their Week 3 diaries on Days 11, 12 and 13 but the actual Day 21 visit occurred on Day 24. All diaries included because the diaries are closest to Day 21 which matches the clinic visit (Week 3).

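### The Day 7 instruction ties the Week 3 diary to the next phone visit, which is the wrong day wherever Week 2 is in clinic and, in Japan, may lead to an early diary

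*Protocol*

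**What the plan says.** Protocol Section 6.2.3 (Day 7) has the site "Dispense OFF time diary, review instructions including requirement to wait until the next phone visit before completion of the diary". The next dispensing is on Day 28 (Section 6.2.6), so the Day 7 diary is the only one available for Week 3.

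Appendix 7 changes the visit types for Japan. The Week 2 and Week 3 "visits during the Titration Period must be conducted as site (in-clinic) visits", and "two phone visits are required a day after both the Day 0 (Randomization) Visit (Day 1) and Week 1 Visit". The second of these calls is nominally Day 8 and may be held as a site visit instead. The extra visits "are to be conducted in addition to the protocol" schedule. The Appendix 7 lists for Days 8, 14 and 21 contain no diary step.

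Other text gives different timing for the same diary:
- Section 6.2.4 (Day 14), in both the phone and the clinic branch: "Review OFF time diary instructions including requirement to complete diary for 3 consecutive days during the following week".
- Section 7.3.1: three consecutive days in the week before the visit, Day 28 excepted.
- Schedule of Activities, footnote 20, for the diary reviewed at Day 28: "the OFF time diary will be completed between Day 14 and Day 21 and brought the next clinic visit".

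SAP Section 3.1, rule 8, accepts a diary day within 7 days before the visit. An earlier day is accepted only if the closest planned visit is the diary's own nominal visit. Example 1 of that rule, "A subject who completed Week 3 diaries on Days 8, 9, and 10 with the actual Week 3 visit occurring on Day 21", ends in exclusion of all three days.

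**The concern.** The Day 7 wording takes for granted that the next phone contact is Day 14. Where Week 2 is in clinic that is false, and a site or subject who follows the wording is sent to another day. In Japan that day is about a week too early. The diary is on paper, so nothing blocks early entries, and a diary already used is not replaced in time for Week 3.

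At stake are the Week 3 OFF and ON times, which are secondary endpoints by visit. An early diary is either lost or counted as Week 3 although it was written in Week 2. Because the visit rules differ by country, any such error would follow region, which is the randomization stratification factor.

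**Working it through.** **1. Which day is the next phone visit after Day 7?**

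| Site practice | Next scheduled phone visit | Week after Day 14, as in Section 6.2.4? |
|---|---|---|
| Week 2 by phone | Day 14 | Yes |
| Week 2 in clinic, Week 3 by phone | Day 21 | No, diary is due by then |
| Weeks 2 and 3 in clinic, outside Japan | Day 42 | No, after the Day 21 collection |
| Japan, Day 8 contact by phone | Day 8 | No, too early |

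Week 1 has a +3 day window (Section 6.2). A Week 1 visit on Days 7 to 10 puts the Japanese call on Days 8 to 11. Later visits are still timed from Day 0, so Week 3 can remain on Day 21.

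**2. Reproducing the SAP examples.** Planned days are -1, 21, 35 and 70. Counting without a Day 0, diary day d lies d days from Baseline and 21 - d days from Week 3.
- Example 1 (visit Day 21): Day 8 is 8 against 13, Day 9 is 9 against 12, Day 10 is 10 against 11. All are nearer Baseline and excluded, as stated.
- Example 2 (visit Day 70): Days 61 and 62 are 9 and 8 days from Day 70 and more than 25 from Day 35. Day 63 is within 7 days. All are kept, as stated.
- Example 3 (visit Day 24): Day 11 is 11 against 10, Day 12 is 12 against 9, Day 13 is 13 against 8. All are kept, as stated.

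Plain subtraction would make Day 10 a tie (11 against 11), so Example 1 relies on there being no Day 0.

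**3. Applying rules 8 to 11 to a Week 3 visit on Day 21**, with B the baseline average and D the OFF time on a diary day:

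| Diary days | Days kept | Week 3 value |
|---|---|---|
| 8-10 | none | missing (rule 11) |
| 9-11 | Day 11 | (B + D11)/2 (rule 10) |
| 10-12 | Days 11, 12 | mean of two (rule 9) |
| 11-13 | all | mean of three, closest-visit clause |
| any three of 14-20 | all | mean of three, 7-day clause |

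In the second row no diary falls between Baseline and Week 3, so the last available week is Baseline. The change is (B + D11)/2 - B = (D11 - B)/2, half of what Day 11 showed.

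**4. Dose level on those days (Table 2).** On Days 8-14 the 3, 7 and 15 mg arms are at 3 mg. From Day 15 the 7 and 15 mg arms are at 7 mg. A diary on Days 11-13 therefore carries the Week 2 level in those two arms. The placebo, 1 mg and 3 mg arms have the same dose in both weeks.

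**5. Reach to Week 10.** Week 3 enters the MMRM as a post-baseline visit (SAP 5.2.2.1), and the MMRM estimates and covariance feed the Bayesian Emax model (SAP 5.2.2.3.2). Rule 10 can also carry a Week 3 average into a later visit that has only one valid day.

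**The case against.** The strongest reply is that the Day 7 text sets an earliest time and does not tell anyone to start. The Day 8 list in Appendix 7 has no diary step, and Day 8 need not be a phone contact. The instruction to complete comes on Day 14 with the right timing. Days 14 and 21 are ordinary Section 6 visits, so the clinic branch applies in Japan, and Section 7.3.1 agrees. The Day 42 reading is so plainly unworkable that sites would probably not take the line literally. The Day 14 to Day 21 clause in footnote 20 covers only the diary brought to Day 28, so it does not itself govern Japan.

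Most of this stands. It makes early completion a possibility, and a reader who infers that Japanese diaries will be a week early goes beyond the text. It does not remove the defect. The Day 14 review comes too late for a diary already filled in, there is no replacement before Day 28, and a site working from the Appendix 7 lists for Days 14 and 21 would see no diary instruction or collection at all.

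**Conclusion.** The Day 7 instruction is wrong wherever Week 2 is a clinic visit, and it cannot be reconciled with Section 6.2.4 or Section 7.3.1. In Japan it opens the way to an early Week 3 diary that the SAP drops, halves or keeps at the Week 2 dose level, depending on the start day. This rests on the nominal days of Table 2, a Week 3 visit on Day 21, and a subject who starts on or soon after the call.

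It is a minor operational error at a titration-period secondary time point, with only indirect reach to Week 10. Its overall size cannot be computed, because neither the number of subjects in Japan nor the share who would start early is given.

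Four stronger readings are not supported:
- *Loss from the Full Analysis Set.* SAP 4.1 requires one post-dose diary measurement. It does not say that a diary left out of a visit average fails to count, and an early-termination visit can supply a diary (Protocol 6.6, SAP 5.3).
- *Wrong dose in general.* Only the 7 and 15 mg arms are affected, and by design the 15 mg arm is at 7 mg in Week 3 anyway.
- *A percentage dilution from the Emax priors.* That assumes the effect follows the current dose within days, while Section 1.5.1 cites a peak at about 8 weeks for other dopaminergic drugs.
- *Treatment bias from region-linked missingness.* The instruction is the same in all blinded arms, so missingness that follows region does not by itself show bias.

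**What to change.** In Section 6.2.3, replace the reference to the next phone visit with: *wait until the Day 14 (Week 2) visit, whether by phone or in clinic, and complete the diary on 3 consecutive days after the day of that visit and before the day of the Week 3 visit.* For visits on Days 14 and 21 this gives Days 15-20, all within the 7-day rule. A window worded as Day 14 to Day 21 would be looser. It admits Day 14, still at the Week 2 dose level, and Day 21, which rule 8 does not count for a visit on that day.

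In Appendix 7, state on Day 8 that the diary is not to be started, add diary instruction review to the Day 14 list, and add diary collection to the Day 21 list.

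The cost is one sentence in Section 6.2.3 and three lines in Appendix 7. No visit, procedure or SAP rule changes.
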